6.3 Rescue Medications & Supportive Care

6.3.1 Supportive Care Guidelines

Participants should receive appropriate supportive care measures as deemed necessary by the treating investigator. Suggested supportive care measures for the management of adverse events with potential immunologic etiology are outlined below and in greater detail in the Events of Clinical Interest guidance document (Appendix B). Where appropriate, these guidelines include the use of oral or intravenous treatment with corticosteroids as well as additional anti-inflammatory agents if symptoms do not improve with administration of corticosteroids. Note that several courses of steroid tapering may be necessary as symptoms may worsen when the steroid dose is decreased. For each disorder, attempts should be made to rule out other causes such as metastatic disease or bacterial or viral infection, which might require additional supportive care. The treatment guidelines are intended to be applied when the investigator determines the events to be related to pembrolizumab.

Note: if after the evaluation the event is determined not to be related, the investigator is instructed to follow the ECI reporting guidance but does not need to follow the treatment guidance (as outlined in the ECI guidance document). Refer to Section 6 for dose modification.

It may be necessary to perform conditional procedures such as bronchoscopy, endoscopy, or skin photography as part of evaluation of the event. Suggested conditional procedures, as appropriate, can be found in the ECI guidance document.

- **Pneumonitis:**

- For **Grade 2 events**, treat with systemic corticosteroids. When symptoms improve to Grade 1 or less, steroid taper should be started and continued over no less than 4 weeks.
- For **Grade 3-4 events**, immediately treat with intravenous steroids. Administer additional anti-inflammatory measures, as needed.
- Add prophylactic antibiotics for opportunistic infections in the case of prolonged steroid administration.

- **Diarrhea/Colitis:**

Participants should be carefully monitored for signs and symptoms of enterocolitis (such as diarrhea, abdominal pain, blood or mucus in stool, with or without fever) and of bowel perforation (such as peritoneal signs and ileus).

- All participants who experience diarrhea/colitis should be advised to drink liberal quantities of clear fluids. If sufficient oral fluid intake is not feasible, fluid and electrolytes should be substituted via IV infusion. For

Grade 2 or higher diarrhea, consider GI consultation and endoscopy to confirm or rule out colitis.

- For **Grade 2 diarrhea/colitis** that persists greater than 3 days, administer oral corticosteroids.
- For **Grade 3 or 4 diarrhea/colitis** that persists > 1 week, treat with intravenous steroids followed by high dose oral steroids.
- When symptoms improve to Grade 1 or less, steroid taper should be started and continued over no less than 4 weeks.

- **Type 1 diabetes mellitus (if new onset, including diabetic ketoacidosis [DKA]) or ≥ Grade 3 Hyperglycemia, if associated with ketosis (ketonuria) or metabolic acidosis (DKA)**

- For **T1DM** or **Grade 3-4 Hyperglycemia**
 - Insulin replacement therapy is recommended for Type I diabetes mellitus and for Grade 3-4 hyperglycemia associated with metabolic acidosis or ketonuria.
 - Evaluate patients with serum glucose and a metabolic panel, urine ketones, glycosylated hemoglobin, and C-peptide.

- **Hypophysitis:**

- For **Grade 2** events, treat with corticosteroids. When symptoms improve to Grade 1 or less, steroid taper should be started and continued over no less than 4 weeks. Replacement of appropriate hormones may be required as the steroid dose is tapered.
- For **Grade 3-4** events, treat with an initial dose of IV corticosteroids followed by oral corticosteroids. When symptoms improve to Grade 1 or less, steroid taper should be started and continued over no less than 4 weeks. Replacement of appropriate hormones may be required as the steroid dose is tapered.

- **Hyperthyroidism or Hypothyroidism:**

Thyroid disorders can occur at any time during treatment. Monitor patients for changes in thyroid function (at the start of treatment, periodically during treatment, and as indicated based on clinical evaluation) and for clinical signs and symptoms of thyroid disorders.

- **Grade 2** hyperthyroidism events (and **Grade 2-4** hypothyroidism):
 - In hyperthyroidism, non-selective beta-blockers (e.g. propranolol) are suggested as initial therapy.
 - In hypothyroidism, thyroid hormone replacement therapy, with levothyroxine or liothyroinine, is indicated per standard of care.
- **Grade 3-4** hyperthyroidism

- Treat with an initial dose of IV corticosteroid followed by oral corticosteroids. When symptoms improve to Grade 1 or less, steroid taper should be started and continued over no less than 4 weeks. Replacement of appropriate hormones may be required as the steroid dose is tapered.
- **Hepatic:**
 - For **Grade 2** events, monitor liver function tests more frequently until returned to baseline values (consider weekly).
 - Treat with IV or oral corticosteroids
 - For **Grade 3-4** events, treat with intravenous corticosteroids for 24 to 48 hours.
 - When symptoms improve to Grade 1 or less, a steroid taper should be started and continued over no less than 4 weeks.
- **Renal Failure or Nephritis:**
 - For **Grade 2** events, treat with corticosteroids.
 - For **Grade 3-4** events, treat with systemic corticosteroids.
 - When symptoms improve to Grade 1 or less, steroid taper should be started and continued over no less than 4 weeks.

Management of Infusion Reactions: Signs and symptoms usually develop during or shortly after drug infusion and generally resolve completely within 24 hours of completion of infusion.

Table 4 below shows treatment guidelines for participants who experience an infusion reaction associated with administration of pembrolizumab (MK-3475).

Table 4 Infusion Reaction Treatment Guidelines

NCI CTCAE Grade	Treatment	Premedication at subsequent dosing
Grade 1 Mild reaction; infusion interruption not indicated; intervention not indicated	Increase monitoring of vital signs as medically indicated until the participant is deemed medically stable in the opinion of the investigator.	None
Grade 2 Requires infusion interruption but responds promptly to symptomatic treatment (e.g., antihistamines, NSAIDS, narcotics, IV fluids); prophylactic medications indicated for <=24 hrs	Stop Infusion and monitor symptoms. Additional appropriate medical therapy may include but is not limited to: IV fluids Antihistamines NSAIDS Acetaminophen Narcotics Increase monitoring of vital signs as medically indicated until the participant is deemed medically stable in the opinion of the investigator. If symptoms resolve within one hour of stopping drug infusion, the infusion may be restarted at 50% of the original infusion rate (e.g., from 100 mL/hr to 50 mL/hr). Otherwise dosing will be held until symptoms resolve and the participant should be premedicated for the next scheduled dose.	Participant may be premedicated 1.5h (\pm 30 minutes) prior to infusion of pembrolizumab (MK-3475) with: Diphenhydramine 50 mg po (or equivalent dose of antihistamine). Acetaminophen 500-1000 mg po (or equivalent dose of antipyretic).

NCI CTCAE Grade	Treatment	Premedication at subsequent dosing
	Participants who develop Grade 2 toxicity despite adequate premedication should be referred to allergy after discussion with the PI.	
Grades 3 or 4 Grade 3: Prolonged (i.e., not rapidly responsive to symptomatic medication and/or brief interruption of infusion); recurrence of symptoms following initial improvement; hospitalization indicated for other clinical sequelae (e.g., renal impairment, pulmonary infiltrates) Grade 4: Life-threatening; pressor or ventilatory support indicated	Stop Infusion. Additional appropriate medical therapy may include but is not limited to: IV fluids Antihistamines NSAIDS Acetaminophen Narcotics Oxygen Pressors Corticosteroids Epinephrine Increase monitoring of vital signs as medically indicated until the participant is deemed medically stable in the opinion of the investigator. Hospitalization may be indicated. Participant is permanently discontinued from further trial treatment administration.	No subsequent dosing

Appropriate resuscitation equipment should be available in the room and a physician readily available during the period of drug administration.

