3.2 Colitis

The following AE terms, if considered \geq Grade 2 or resulting in dose modification or use of systemic steroids to treat the AE, are considered ECIs and should be reported to the Sponsor within 24 hours of the event:

- Colitis
- Colitis microscopic
- Enterocolitis
- Enterocolitis hemorrhagic
- Gastrointestinal perforation
- Intestinal obstruction
- Necrotizing colitis
- Diarrhea

All attempts should be made to rule out other causes such as metastatic disease, bacterial or parasitic infection, viral gastroenteritis, or the first manifestation of an inflammatory bowel disease by examination for stool leukocytes, stool cultures, a Clostridium difficile titer and endoscopy. However the AE should be reported regardless of etiology.

Course of Action

Grade 2 Diarrhea/Colitis (4-6 stools/day over baseline, dehydration requiring IV fluids $<$ 24 hours, abdominal pain, mucus or blood in stool):

- Report as ECI
- Hold pembrolizumab.
- Symptomatic Treatment
- For Grade 2 diarrhea that persists for greater than 3 days, and for diarrhea with blood and/or mucus,
 - Consider GI consultation and endoscopy to confirm or rule out colitis
 - Administer oral corticosteroids (prednisone 1-2 mg/kg QD or equivalent)
- When symptoms improve to Grade 1 or less, steroid taper should be started and continued over no less than 4 weeks.
- Permanently discontinue for inability to reduce corticosteroid dose to 10 mg or less of prednisone or equivalent per day within 12 weeks.
- If symptoms worsen or persist $>$ 3 days treat as Grade 3

Grade 3 Diarrhea/Colitis (or Grade 2 diarrhea that persists for $>$ 1 week):

- Report as ECI
- Hold pembrolizumab.
- Rule out bowel perforation. Imaging with plain films or CT can be useful.
- Recommend consultation with Gastroenterologist and confirmation biopsy with endoscopy.
- Treat with intravenous steroids (methylprednisolone 125 mg) followed by high dose oral steroids (prednisone 1 to 2 mg/kg once per day or dexamethasone 4 mg every 4 hours) When symptoms improve to Grade 1 or less, steroid taper should be started and continued over no less than 4 weeks. Taper over 6 to 8 weeks in patients with diffuse and severe ulceration and/or bleeding.
- Permanently discontinue for inability to reduce corticosteroid dose to 10 mg or less of prednisone or equivalent per day within 12 weeks.

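### Section 6.3.1 sets a later steroid trigger for Grade 3-4 diarrhea/colitis (more than 1 week) than for Grade 2 (more than 3 days), and Appendix B 3.2 states no wait for Grade 3 or 4

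*Combined protocol and SAP*

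**What the plan says.** Section 6.3.1 lists suggested measures for adverse events of possible immune origin. It opens by leaving care to clinical judgment: "Participants should receive appropriate supportive care measures as deemed necessary by the treating investigator". Its diarrhea/colitis block has two steroid lines:

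- Grade 2: disease "that persists greater than 3 days, administer oral corticosteroids".
- Grade 3 or 4: disease "that persists > 1 week, treat with intravenous steroids followed by high dose oral steroids".

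No other line in 6.3.1 says when steroids start for Grade 3-4 diarrhea/colitis.

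Appendix B 3.2 covers the same event in more detail. The heading of its Grade 3 block begins "Grade 3 Diarrhea/Colitis (or Grade 2 diarrhea that persists for" and goes on to give a duration of more than 1 week, which qualifies Grade 2 diarrhea. Under that heading, intravenous methylprednisolone is followed by high dose oral steroids, with no duration attached to Grade 3. Grade 4 is managed in the same way.

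**The concern.** One expects the threshold for starting steroids to fall, or at least not rise, as severity rises. Here it rises: moderate disease qualifies after 3 days and severe or life-threatening disease only after a week. The protocol's own appendix has no such wait.

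The stake is patient safety. Immune-mediated colitis is a listed pembrolizumab reaction (Section 7.1.2), and 6.3.1 itself tells sites to watch for bowel perforation. Read literally, the Grade 3-4 line leaves the sicker patients without a steroid instruction during the first week. No statistical property of the trial is involved.

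**Working it through.** The plan states no figure to reproduce here, so the check is a comparison of texts.

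**Triggers within diarrhea/colitis**

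| Grade | Section 6.3.1 | Appendix B 3.2 |
|---|---|---|
| 2 | oral steroids after more than 3 days | oral steroids after more than 3 days, or with blood or mucus; one line says treat as Grade 3 if worse or beyond 3 days, while the Grade 3 heading says beyond 1 week |
| 3 | IV then high dose oral after more than 1 week | IV then high dose oral, no stated wait |
| 4 | as Grade 3 | as Grade 3 |

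In 6.3.1 the Grade 3-4 trigger is 7 − 3 = 4 days later than the Grade 2 trigger. In Appendix B the one-week duration belongs to Grade 2. It may have been moved to the wrong grade when 6.3.1 was written, but the documents do not confirm that.

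Appendix B 3.2 also says to consider further anti-inflammatory treatment if IV then high dose oral steroids have not reduced initial symptoms within 48 to 72 hours. A Grade 3 patient treated at onset could therefore be considered for second-line treatment by day 2 or 3. On the literal 6.3.1 line, first-line steroids would start only after day 7.

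**Persistence conditions across event types directed to steroids**

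| Event | 6.3.1, Grade 3-4 | Appendix B, Grade 3 |
|---|---|---|
| Pneumonitis | none: "immediately treat with intravenous steroids. Administer additional anti-inflammatory measures, as needed" | none (3.1) |
| Diarrhea/colitis | more than 1 week | none (3.2) |
| Hypophysitis | none: "treat with an initial dose of IV corticosteroids followed by oral corticosteroids" | none (3.3) |
| Hyperthyroidism | none | none (3.3) |
| Hepatic | none: "treat with intravenous corticosteroids for 24 to 48 hours" | none (3.5) |
| Renal | none: "treat with systemic corticosteroids" | none (3.8) |
| **Count** | **1 of 6** | **0 of 6** |

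Appendix B is counted at Grade 3 because it has no Grade 4 line for hypophysitis.

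**Which text governs**

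1. Section 6.2 sends the reader to both 6.3.1 and Appendix B for supportive care, naming corticosteroids. Section 6.3.1 says Appendix B has the greater detail.
2. The Overview of Appendix B (Section 1) says that questions on dose modification or other treatment options are settled by the protocol's specific wording.
3. The references are circular. A reader who follows step 2 returns to the one-week line.

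**Does the wait serve attribution?** Section 6.3.1 says its treatment guidelines apply once the investigator judges the event related to pembrolizumab. The one-week condition therefore applies after attribution, and the documents give no reason for it.

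**The case against.** The strongest reply is that this is advisory text with a better version close at hand. The measures are suggested and left to the treating investigator, and Appendix B also invokes individual judgment. Section 5.5.3 permits systemic steroids for events of clinical interest of suspected immune origin, so nothing forbids starting earlier. Sections 6.2 and 6.3.1 both point to Appendix B, which has no wait. Harm requires a site to read one line literally and set the rest aside. All of this stands as a limit on the claim. It does not remove the conflict, because Appendix B sends treatment questions back to the protocol.

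Other safeguards exist:

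- Table 3 holds pembrolizumab for Grade 2-3 diarrhea/colitis and stops it for Grade 4.
- Section 6.3.1 asks for monitoring for perforation, fluids, and consideration of gastroenterology consultation and endoscopy.
- Appendix B 3.2 requires reporting of Grade 2 or higher events within 24 hours, and for Grade 3 asks sites to rule out perforation and recommends a gastroenterology consultation.
- Section 5.6 requires immediate notice to the Overall PI of life-threatening complications.

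These reduce the risk, but apart from Appendix B's own conflicting instruction, none says when steroids should start. Section 6.2 also notes that immune events can appear months after the last dose, when holding the drug no longer helps.

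A third point is that the count across event types is weak evidence. Colitis is also the event in 6.3.1 with a persistence condition at Grade 2, and diarrhea is non-specific: PLD commonly causes it (Section 7.1.1), and Section 5.4 excludes from DLTs Grade 3 diarrhea controlled within 24 hours. This is partly right. The comparison between Grade 2 and Grade 3-4 within colitis carries the argument, and the count only supports it. Non-specificity could explain some delay, but not a longer delay for the more severe grades.

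Finally, nothing here touches the endpoint, alpha, power or sample size. That is correct, and no such effect is claimed.

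**Conclusion.** The point holds. Section 6.3.1 makes steroids for Grade 3-4 diarrhea/colitis conditional on more than 1 week of persistence, against more than 3 days for Grade 2, and conflicts with Appendix B 3.2. The line is wrong as written and should be corrected, because followed literally it delays treatment in the sicker patients.

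The conclusion rests on reading the Grade 3-4 line as a condition for starting steroids, which is its plain sense, and on the absence of any other start instruction for those grades in 6.3.1. The clinical consequence cannot be sized: the documents give neither a rate of Grade 3-4 colitis nor data on the effect of steroid timing. This is a correction to safety text, not a flaw in the statistical design.

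**What to change.** Delete the one-week persistence condition from the Grade 3-4 diarrhea/colitis line in Section 6.3.1. The line should then direct sites to start intravenous steroids, followed by high dose oral steroids, for Grade 3 or 4 disease with no minimum duration of symptoms. That matches Appendix B 3.2. The sponsor's clinicians should confirm the wording.

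The Grade 2 lines are left as they are. Appendix B's own inconsistency on when Grade 2 escalates (more than 3 days in one line, more than 1 week in the Grade 3 heading) is not resolved by this change.

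The cost is one line in a protocol amendment, with no change to design, sample size or analysis.

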Grade 2: Painful erythema, edema or ulcers but can eat.	
 • Delay dosing up to 2 weeks or until resolved to grade 0 or 1. • Discontinue doxil if no resolution after 2 weeks. • If resolved to grade 0 or 1 within 2 weeks: 
and no previous grade 3 or 4 HFS, continue treatment at previous dose
 
or
 
And previous Grade 3 or 4 toxicity; decrease dose by 25%

Grade 3: Painful erythema, edema or ulcers and cannot eat.	
 • Delay dosing up to 2 weeks or until resolved to grade 0 or 1. Decrease dose by 25% and return to original dose interval • Discontinue doxil if no resolution after 2 weeks
Grade 4: Diffuse or local process causing infectious complications, or a bed ridden state or	
 • Delay dosing up to 2 weeks or until resolved to grade 0 or 1, then decrease dose by 25% and

hospitalization.	
 return to original dose interval • Discontinue doxil if no resolution after 2 weeks
------------------	--

Neutropenia and Thrombocytopenia

Toxicity	Dose Adjustment
Neutropenia and Thrombocytopenia	
Grade 1	No dose reduction
Grade 2	Delay until ANC \geq 1500 and plts \geq 100,000; resume treatment at previous dose
Grade 3	Delay until ANC \geq 1500 and plts \geq 100,000; resume treatment at previous dose
Grade 4	Delay until ANC \geq 1500 and plts \geq 100,000; resume at 25% dose reduction or continue previous dose with prophylactic granulocyte growth factor.

6.2 Dose Modifications for Pembrolizumab:

Adverse events (both non-serious and serious) associated with pembrolizumab exposure may represent an immunologic etiology. These adverse events may occur shortly after the first dose or several months after the last dose of treatment. Pembrolizumab must be withheld for drug-related toxicities and severe or life-threatening AEs as per Table 3 below. See Section 6.3.1 and Events of Clinical Interest Guidance Document for supportive care guidelines (**Appendix B**), including use of corticosteroids.

Table 3

Dose Modification Guidelines for Drug-Related Adverse Events (Please also see Appendix B)

Toxicity	Hold Treatment For Grade	Timing for Restarting Treatment	Discontinue Participant

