Diarrhea/Colitis	2-3	Toxicity resolves to Grade 0-1.	Toxicity does not resolve within 12 weeks of last dose or inability to reduce corticosteroid to 10 mg or less of prednisone or equivalent per day within 12 weeks.
	4	Permanently discontinue	Permanently discontinue
AST, ALT, or Increased Bilirubin	2	Toxicity resolves to Grade 0-1	Toxicity does not resolve within 12 weeks of last dose.
	3-4	Permanently discontinue (see exception below) ¹	Permanently discontinue
Type 1 diabetes mellitus (if new onset) or	T1DM or 3-4	Hold pembrolizumab for new onset Type 1 diabetes mellitus or Grade 3-4 hyperglycemia associated	Resume pembrolizumab when patients are clinically and metabolically stable.

Toxicity	Hold Treatment For Grade	Timing for Restarting Treatment	Discontinue Participant
Hyperglycemia		with evidence of beta cell failure.	
Hypophysitis	2-3	Toxicity resolves to Grade 0-1	Toxicity does not resolve within 12 weeks of last dose or inability to reduce corticosteroid to 10 mg or less of prednisone or equivalent per day within 12 weeks.
	4	Permanently discontinue	Permanently discontinue
Hyperthyroidism	3	Toxicity resolves to Grade 0-1	Toxicity does not resolve within 12 weeks of last dose or inability to reduce corticosteroid to 10 mg or less of prednisone or equivalent per day within 12 weeks.
	4	Permanently discontinue	Permanently discontinue
Hypothyroidism	2-4	Therapy with pembrolizumab can be continued while treatment for the thyroid disorder is instituted	Therapy with pembrolizumab can be continued while treatment for the thyroid disorder is instituted.
Infusion Reaction	3-4	Permanently discontinue	Permanently discontinue
Pneumonitis	2	Toxicity resolves to Grade 0-1	Toxicity does not resolve within 12 weeks of last dose or inability to reduce corticosteroid to 10 mg or less of prednisone or equivalent per day within 12 weeks.
	3-4	Permanently discontinue	Permanently discontinue
Renal Failure or Nephritis	2	Toxicity resolves to Grade 0-1	Toxicity does not resolve within 12 weeks of last dose or inability to reduce corticosteroid to 10 mg or less of prednisone or equivalent per day within 12 weeks.
	3-4	Permanently discontinue	Permanently discontinue
All Other Drug-Related Toxicity ²	3 or Severe	Toxicity resolves to Grade 0-1	Toxicity does not resolve within 12 weeks of last dose or inability to reduce corticosteroid to 10 mg or less of prednisone or equivalent per day within 12 weeks.
	4	Permanently discontinue	Permanently discontinue

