In most patients, these reactions resolve over the course of several hours to a day once the infusion is terminated. Serious and sometimes life-threatening or fatal allergic/anaphylactoid-like infusion reactions have been reported. Medications to treat such reactions, as well as emergency equipment, should be available for immediate use.

The majority of infusion-related events occurred during the first infusion. Similar reactions have not been reported with conventional doxorubicin and they presumably represent a reaction to the DOXIL liposomes or one of its surface components. The initial rate of infusion should be 1 mg/min to help minimize the risk of infusion reactions.

3) Radiation recall: can rarely occur.

4) Fetal mortality: Most of our patients will not be child-bearing and if they are, eligibility requirements require use of contraception.

7.1.2 Pembrolizumab:

The most common adverse reactions (reported in $\geq 20\%$ of patients) include: Fatigue, cough, nausea, pruritus, rash, decreased appetite, constipation, arthralgia, and diarrhea.

Immune-mediated adverse reactions include the following:

- Immune-mediated pneumonitis
- Immune-mediated colitis
- Immune-mediated hepatitis
- Immune-mediated hypophysitis
- Immune-mediated nephritis
- Immune-mediated hyperthyroidism and hypothyroidism
- Embryofetal toxicity

Other more rare toxicities include:

1) Immune-mediated adverse reactions occurred in less than 1% of patients, and include the

following : exfoliative dermatitis, uveitis, arthritis, myositis, pancreatitis, hemolytic anemia, partial seizures arising in a patient with inflammatory foci in brain parenchyma, and adrenal insufficiency. Across clinical studies with pembrolizumab, in approximately 2000 patients, the following additional clinically significant, immune-mediated adverse reactions were reported in less than 1% of patients: myasthenic syndrome, optic neuritis, and rhabdomyolysis.

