10. STUDY CALENDAR

Baseline evaluations are to be conducted within 14 days prior to start of protocol therapy. Baseline labs must be performed within 14 days of treatment initiation. Scans and x-rays must be done ≤ 4 weeks prior to the start of therapy. In the event that the participant's condition is deteriorating, laboratory evaluations should be repeated within 48 hours prior to initiation of the next cycle of therapy.

Assessments must be performed prior to administration of any study agent. Study assessments and agents should be administered within ± 3 days of the protocol-specified date, unless otherwise noted.

	Pre-Study	C1 D1	C1 D8	C1 D15	C1 D22	C2 D1	C2 D15	C3 D1	C3 D8	Cycle 4 and beyond^f	Off Study ^c
PLD ^d		A				A		A		A	
Pembrolizumab ^e		B			B		B		B	B	
Informed consent	X										
Demographics	X										
Medical history	X										
Concurrent meds	X	X-								X ^f	
Physical exam ¹	X	X			X	X	X	X	X	X ^f	X
Vital signs ²	X	X			X	X	X	X	X	X ^f	X
Height and weight ³	X	X			X	X	X	X	X	X ^f	
Performance status ⁴	X	X			X	X	X	X	X	X ^f	X
CA-125	X	X				X		X			X
CBC w/diff, plts	X	X	X	X	X	X	X	X	X	X ^f	X
Serum chemistry ^a	X	X	X	X	X	X	X	X	X	X ^f	X
TSH	X	X				X					X
EKG (as indicated)	X										
Adverse event evaluation		X-								X ^f	X
Tumor measurements	X	Tumor measurements are repeated every 8 weeks ± 1 week weeks. Documentation (radiologic) must be provided for participants removed from study for progressive disease. ^g									X
B-HCG	X ^b										
FFPE blocks ^d	X										
ECHO or MUGA ^e	X									X ^e	

A: PLD 40 mg/m² IV every 28 days ± 3 days window

B: Pembrolizumab 200 mg IV every 21 days ± 3 days window

1: Will include skin examination in addition to physical exam

2: Including blood pressure, temperature, respiratory rate, heart rate

3: Height should be performed at screening and Cycle 1 Day 1 only, weight should be performed at each visit

4: ECOG performance status as per Appendix 1.

5: The schedules for pembrolizumab and doxil can be delayed independently, however, the clock does not stop for each 28 day cycle regarding the cycle/day.

- a: Albumin, alkaline phosphatase, total bilirubin, bicarbonate, BUN, calcium, chloride, creatinine, glucose, LDH, phosphorus, potassium, total protein, SGOT [AST], SGPT [ALT], sodium.
- b: Serum pregnancy test (only for women of childbearing potential).

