- c: Off-study evaluation. Patients will be followed for 4 weeks post treatment for adverse events. Patients will be followed for survival every 3 months for two years or until death, whichever occurs first.
- d: Obtained as part of eligibility criteria and will include PDL1 and nanostring analysis
- e: Up to a week before cycle 4 of PLD, and subsequent cycles (every 3 cycles).
- f: Physical exam, vital signs, PS as well as the following labs: CBC with plts, serum chemistry should be performed on a treatment day regardless if patients are receiving PLD alone, pembrolizumab alone or both agents.
- g: Immunotherapeutic agents such as pembrolizumab may produce antitumor effects by potentiating endogenous cancer-specific immune responses. The response patterns seen with such an approach may extend beyond the typical time course of responses seen with cytotoxic agents and can manifest a clinical response after an initial increase in tumor burden or even the appearance of new lesions. Patients with initial PD will be allowed to stay on trial with a repeat scan in 4 weeks. If repeat imaging confirms PD, patients will be discontinued from study therapy.

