3.3 Endocrine

The following AE terms, if considered \geq Grade 3 or if \geq Grade 2 and require holding/discontinuation/ modification of pembrolizumab dosing, are considered ECIs and should be reported to the Sponsor within 24 hours of the event:

- Adrenal insufficiency
- Hyperthyroidism
- Hypophysitis
- Hypopituitarism
- Hypothyroidism
- Thyroid disorder
- Thyroiditis

All attempts should be made to rule out other causes such as brain metastases, sepsis and/or infection. However the AE should be reported regardless of etiology.

Hypophysitis or other symptomatic endocrinopathy other than hypo- or hyperthyroidism

Grade 2-3 events:

- Report as ECI if appropriate
- Hold pembrolizumab
- Rule out infection and sepsis with appropriate cultures and imaging.
- Monitor thyroid function or other hormonal level tests and serum chemistries more frequently until returned to baseline values.
- Pituitary gland imaging should be considered (MRIs with gadolinium and selective cuts of the pituitary can show enlargement or heterogeneity and confirm the diagnosis).
- Treat with prednisone 40 mg p.o. or equivalent per day. When symptoms improve to Grade 1 or less, steroid taper should be started and continued over no less than 4 weeks. Replacement of appropriate hormones may be required as the steroid dose is tapered.
- Permanently discontinue for inability to reduce corticosteroid dose to 10 mg or less of prednisone or equivalent per day within 12 weeks.
- Hypophysitis with clinically significant adrenal insufficiency and hypotension, dehydration, and electrolyte abnormalities (such as hyponatremia and hyperkalemia) constitutes adrenal crisis.
- Consultation with an endocrinologist may be considered.

Hyperthyroidism and Hypothyroidism

Thyroid disorders can occur at any time during treatment. Monitor patients for changes in thyroid function (at the start of treatment, periodically during treatment, and as indicated based on clinical evaluation) and for clinical signs and symptoms of thyroid disorders.

Grade 2 hyperthyroidism, Grade 2-4 hypothyroidism events:

- Report as ECI if appropriate (see Table 1)
- Monitor thyroid function or other hormonal level tests and serum chemistries more frequently until returned to baseline values.
- Thyroid hormone and/or steroid replacement therapy to manage adrenal insufficiency.
- Therapy with pembrolizumab can be continued while treatment for the thyroid disorder is instituted.

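### The study calendar schedules no on-treatment TSH after Cycle 2 Day 1, short of the periodic thyroid monitoring the protocol itself calls for

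*Combined protocol and SAP*

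**What the plan says.** **The instruction.** Section 6.3.1, under hyperthyroidism or hypothyroidism: "Monitor patients for changes in thyroid function (at the start of treatment, periodically during treatment, and as indicated based on clinical evaluation". Appendix B 3.3 gives the same instruction and the reason for it: "Thyroid disorders can occur at any time during treatment". There are three limbs: a baseline, periodic testing on treatment, and testing prompted by clinical findings. No interval is given for the second.

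**The schedule.** In the Section 10 calendar, TSH is marked at Pre-Study, C1D1, C2D1 and Off Study. The cells for C1D8, C1D15, C1D22, C2D15, C3D1, C3D8 and Cycle 4 and beyond are empty. Note f governs later treatment days and says that "the following labs: CBC with plts, serum chemistry should be performed on a treatment day"; it does not name TSH. Note a lists the serum chemistry panel, which contains no thyroid test. No other section schedules a thyroid test for a patient who has not already had a thyroid event.

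**The concern.** The calendar and Section 6.3.1 give sites different pictures of the same safety task. One test after the first dose is hard to call periodic when Section 5.6 allows 35 pembrolizumab treatments over about two years.

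The toxicity is a recognised one. Section 7.1.2 lists among the immune-mediated reactions "Immune-mediated hyperthyroidism and hypothyroidism". Section 6.2 says of immune-related events: "These adverse events may occur shortly after the first dose or several months after the last dose of treatment". A test at day 29 cannot stand in for the rest of treatment.

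Several actions depend on detection:

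- Table 3 holds pembrolizumab for Grade 3 hyperthyroidism and stops it at Grade 4.
- Section 6.3.1 describes treatment for both thyroid disorders.
- Appendix B requires 24-hour reporting of thyroid events at Grade 3 or above, or at Grade 2 or above in defined circumstances such as a dose modification.

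Toxicity is also a secondary endpoint, summarised under Section 13.5 by term and maximum grade, so what is not tested for may not be counted.

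**Working it through.** The plan states no figure to reproduce here. The check is a reading of the calendar followed by a count of days.

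**Reading the calendar.** The table has 11 columns and the TSH row has 11 cells, with marks in the Pre-Study, C1D1, C2D1 and Off Study positions. The CA-125 row, aligned the same way, carries an additional mark at C3D1. Note f independently leaves TSH out of the later treatment-day labs. A misread table is therefore unlikely.

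**Inputs.**

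- Pembrolizumab every 21 days (Section 5.3.2.1), so undelayed doses fall on day 1 + 21k: 1, 22, 43, 64, 85, 106, 127, 148 and so on.
- 28-day cycles (Section 5.1), so C2D1 is day 29 and C3D8 is day 64.
- A cap of 35 pembrolizumab treatments (Section 5.6).
- PFS of about 3-4 months on PLD (Section 2.2), used as a stand-in for typical treatment duration. This is an assumption, since the figure is for PLD and not the combination. Three and four months are taken as days 91 and 122.

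**Time after the last scheduled on-treatment TSH (day 29), no delays.** For treatment to day D, the interval is D - 29 days and its share of treatment time is (D - 29)/(D - 1).

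| Treated to | Interval | Share of treatment time | Pembrolizumab doses after day 29 |
|---|---|---|---|
| Day 91 | 62 d = 8.9 wk | 62/90 = 69% | 3 of 5 |
| Day 122 | 93 d = 13.3 wk | 93/121 = 77% | 4 of 6 |
| Day 168 (24 wk) | 139 d = 19.9 wk | 139/167 = 83% | 6 of 8 |
| Dose 35: day 1 + 34 × 21 = 715 | 686 d = 98.0 wk | 686/714 = 96% | 33 of 35 |

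Few patients are likely to reach the last row. The first two describe the ordinary patient.

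**What the example fix would give.** Tests on days 64 + 42k fall on days 64, 106, 148 and so on, all undelayed pembrolizumab days.

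- Tests per patient: 1 by day 91, 2 by day 122, 3 by day 168, 16 by day 715.
- Gaps: 64 - 29 = 35 days (5 weeks), then 42 days (6 weeks). If one test is 3 days early and the next 3 days late, 42 + 6 = 48 days.

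**The case against.** **The guidance is soft and the two texts can be followed together.** Section 6.3.1 opens with: "Suggested supportive care measures for the management of adverse events with potential immunologic etiology are outlined below". It sets no interval, nothing says the calendar displaces it, and a site may order TSH at any visit. A reader might infer that the protocol contradicts itself or rules out later testing. The documents do not support that: the calendar is silent and does not prohibit. What remains is that the schedule, followed to the letter, does not deliver the second limb of the instruction. Clinically indicated testing is a separate limb and does not supply it.

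**The interval is closed by a test.** The Off Study TSH comes at the end, and adverse events are followed for 4 weeks after treatment (Section 5.7). An abnormality still present would be found and could enter the toxicity summary. This stands. It narrows the under-counting to events that appear and resolve between draws, or whose peak grade is missed. It does not help management on treatment.

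**The consequence is modest.** Physical examination, vital signs, chemistry and adverse event evaluation continue. Under Table 3, hypothyroidism does not stop pembrolizumab, and hyperthyroidism does so only from Grade 3. This also stands.

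**The percentages measure time, not harm.** Correct. A reader might take 69-77% as the share of thyroid events missed, or conclude that the toxicity summary is seriously biased. The documents give no thyroid event rate, so neither can be derived.

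**Conclusion.** The point holds as a shortfall between the calendar and the protocol's own guidance. After day 29 no on-treatment TSH is scheduled. That leaves 69-77% of treatment time beyond the last such test for a patient treated for 3-4 months, and up to 33 of 35 doses (98 weeks) at the cap. These figures assume undelayed dosing, and the 3-4 months is borrowed from PLD.

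The main effect is late detection of asymptomatic thyroid events. Under-ascertainment in the Section 13.5 summary is limited, and the number of patients affected cannot be estimated.

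One might be tempted to extend the point to the trial's decision rules; it does not reach them. The DLT window is the first 4 weeks, and the untested interval begins after C2D1. Clinical benefit is judged by RECIST and duration of stable disease, so the 10-of-26 rule does not depend on TSH. This is a cheap improvement to safety monitoring.

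**What to change.** Mark TSH in the C3D8 and Cycle 4 and beyond columns and give it its own footnote, as note e does for ECHO/MUGA. Do not simply add it to note f: that note is triggered by any treatment day, so it would call for a TSH at every infusion visit and none during a hold.

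The footnote should state an interval, chosen by the sponsor, that applies while the patient is on pembrolizumab, including during holds. An example, which is my assumption and not a figure from the protocol, is every 6 weeks: study days 64, 106, 148 and every 42 days after, within the usual 3-day window.

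Fixed study days are preferable to counting doses. Calendar note 5 says that "the clock does not stop for each 28 day cycle regarding the cycle/day", so the test days stay defined during a hold. The discontinuation limit in Table 3 ("Toxicity does not resolve within 12 weeks of last dose") allows long holds. A test at every second dose could then leave 12 + 3 = 15 weeks between tests after a single hold to that limit.

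**Cost.** A calendar edit and, at the example interval, 1-2 assays per patient treated for 3-4 months, or 26-52 if all 26 patients were treated that long (26 × 1 to 26 × 2). A patient treated to day 168 would need 3, and one reaching dose 35 without delay would need 16. With undelayed dosing every test falls on a pembrolizumab day when blood is already drawn. During a hold an occasional extra draw may be needed.
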